WAYNE STATE
UNIVERSITY

EUGENE APPLEBAUM
COLLEGE OF PHARMACY
AND HEALTH SCIENCES

Study Title: Telephone-Delivered Exercise for Multiple Sclerosis Fatigue

NCT Number: NCT03256851

Document Date: February 8, 2018

Study Protocol

The specific objectives of this study were to determine: a) the feasibility and acceptability of a telephone-delivered exercise intervention to target fatigue in persons with MS; and b) how the telephone-based exercise intervention compared in absolute terms to an otherwise identical in-person-delivered exercise intervention in pre- to post-treatment changes in fatigue and secondary outcomes.

Inclusion/Exclusion Criteria. A trained research coordinator completed a telephone screening form with each participant. The study PIs then determined whether the individual met the study inclusion and exclusion criteria. Participants were included if they had a diagnosis of MS, were independently ambulatory with or without an assistive device for at least 5 minutes at a time, had significant fatigue as indicated by a score of ≥ 36 (of 63 possible points, for an average fatigue score of 4/7 points) on the Fatigue Severity Scale (FSS), and were able to follow study related commands. Participants were excluded if they were experiencing any of the following: MS exacerbation within the past 30 days, an additional neurological condition that affected walking, or pregnancy.

Randomization and Allocation Concealment. Eligible participants were consented and randomly assigned into the telephone-delivered exercise group (telephone; n=10) or the in-person-delivered exercise group (in-person; n=10). Simple randomization (i.e., single random number sequence) using SPSS was performed by the UM study team, who were not involved in participant testing or training. To ensure concealed allocation, sealed envelopes with group assignment were given to the study team at WSU and pulled sequentially at the time of randomization.

Testing Sessions. At baseline visit 1, participants completed informed consent procedures and surveys using Qualtrics, a free online research tool licensed by WSU which enables the creation of study-specific websites for securely entering and storing participant data. Gait speed was assessed and resting heart rate (HR) was obtained for calculation of target HR for week 1. Participants were outfitted with a PRO-Diary accelerometer and asked to continue their usual activities for the next week. One week after visit 1, participants returned to the lab for baseline visit 2 where they returned their accelerometer, and were randomized into either telephone or in-person group. Eight weeks later, after the intervention was

finished, participants completed a post-treatment testing session, which included Qualtrics surveys, gait speed assessment, and donning of a PRO-Diary to wear for the next week. Participants returned PRO-Diaries to the lab in a pre-paid box.

In-person Training. Participants in the in-person group received 1x/wk training with a physical therapist or trained member of the research team (e.g., doctoral physical therapy student). Training sessions consisted of 30 minutes of endurance training and 30 minutes of strength training, focusing on progression of exercises and review of weekly module. Participants followed a home exercise program for the remainder of the week.

Telephone Training. Participants in the telephone group received a 1x/week telephone call from a physical therapist. Participants reviewed the weekly module, reported their progress from the prior week, discussed any issues or problems, and received progressions of exercises for the upcoming week.

Statistical Analysis Plan

All analyses were performed using Stata (version 15.1, StataCorp LLC, College Station, TX). Normally distributed continuous variables were described by means and standard deviations (SD), non-normally distributed variables by medians and interquartile ranges (IQR), and categorical variables by number and percentages. Mean change scores (SD) (pre-post intervention) were calculated for each variable by intervention group and Cohen's *d* effect sizes were computed (mean change divided by standard deviation of the mean change). Effect sizes for fatigue-related outcome measures were used to calculate a minimum sample size for a two-tailed t-test study with a probability level of 0.05 and desired statistical power of 0.8. Between-group differences were analyzed using a two-sample t test to generate mean differences and 95% confidence intervals. Pre- and post-intervention fatigue scores (fatigue intensity, interference) were plotted by group, for each participant and for the group mean.

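### Does it matter that the feasibility and acceptability objective has no named measure, denominator or criterion?

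*Combined protocol and SAP*

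**What the plan says.** The objectives paragraph of the Study Protocol gives objective (a) as "the feasibility and acceptability of a telephone-delivered exercise intervention to target fatigue in persons with MS". Objective (b) compares the two modes of delivery on pre-to-post change in fatigue and secondary outcomes. Objective (a) is not mentioned again by name.

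The SAP opens with general rules for describing data. They name no variable, and they include "categorical variables by number and percentages" as well as medians with interquartile ranges for skewed quantities. Its specific outputs are:

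- change scores ("Mean change scores (SD) (pre-post intervention) were calculated for each variable by intervention group");
- Cohen's *d* from those changes;
- a sample size for a later study, based on the fatigue effect sizes;
- a two-sample t test with a mean difference and confidence interval;
- plots of fatigue scores before and after treatment.

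Several described steps could supply feasibility data, although none is labelled as such:

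- Inclusion/Exclusion Criteria: "A trained research coordinator completed a telephone screening form with each participant".
- Testing Sessions: "One week after visit 1, participants returned to the lab for baseline visit 2", where randomisation took place; and, after the intervention, "participants completed a post-treatment testing session, which included Qualtrics surveys".
- Telephone Training: "Participants in the telephone group received a 1x/week telephone call from a physical therapist", in which participants "reported their progress from the prior week, discussed any issues or problems".

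**The concern.** An objective without a named outcome leaves the analyst free to choose one after seeing the data. The general rule fixes how a count is shown. It does not fix which count is shown, or over which people. A participant with no post-treatment data has no change score, so none of the specific SAP outputs counts non-completion or adherence. Read to the letter, the plan could report objective (b) in full and leave (a) without a result.

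With 10 people in the telephone arm, the choice of measure and threshold could also decide whether the programme is called feasible. If so, the conclusion on the leading objective would depend on a decision that the documents do not record.

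**Working it through.** **What is and is not in the text.** There is no derivation to reproduce. The group size of 10 is given without inputs, and no feasibility figure is stated. The first check is therefore whether the usual feasibility quantities can be formed from the described steps and the existing descriptive rule.

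| Quantity | Where it comes from | Rule that covers it |
|---|---|---|
| Screened, eligible | telephone screening form, eligibility decision | count, percentage |
| Consented, randomised | baseline visit 1, baseline visit 2 | count, percentage |
| Assessed after treatment, out of 10 per arm | post-treatment session | count, percentage |
| Calls completed, out of 8 (one a week for eight weeks) | weekly calls, if logged | median, IQR |
| Acceptability | post-treatment surveys, if items were included | count, percentage, or median, IQR |

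The first three rows follow from steps the protocol describes. The last two depend on records that the documents do not show, and extra SAP wording cannot create those records. Loss to assessment also follows by subtraction: 10 minus the number analysed in that arm.

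**How large the concern looks if a pass mark is assumed.** Every rate and cut below is an assumption; the documents give none.

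*Threshold.* Let X ~ Bin(10, *p*) be the number retained, with a pass if X ≥ *k*.

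| True retention *p* | *k* = 7 | *k* = 8 | *k* = 9 |
|---|---|---|---|
| 0.7 | 0.650 | 0.383 | 0.149 |
| 0.8 | 0.879 | 0.678 | 0.376 |
| 0.9 | 0.987 | 0.930 | 0.736 |

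*Definition of adherent.* Let Y ~ Bin(8, *q*) be the calls completed, treated as independent. At *q* = 0.85, P(Y ≥ 6, 7, 8) = 0.895, 0.657, 0.272. The corresponding values are 0.797, 0.503, 0.168 at *q* = 0.80 and 0.962, 0.813, 0.430 at *q* = 0.90. The median is 7 of 8 calls for all three values of *q*, so a plain median with IQR avoids the choice of cut.

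*Best of three measures.* With *p* = 0.7 for each and a cut of 8 of 10, a single measure passes with probability 0.383. Three independent measures give 1 − (1 − 0.383)³ = 0.765. With latent within-person correlation of 0.3, 0.5 and 0.7, simulation gives 0.714, 0.676 and 0.629; at 0.9 the figure is about 0.55. Nothing in the documents indicates which correlation applies.

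These three calculations matter only if the programme is to be declared feasible or not against a cut. The plan contains no such declaration. If estimates alone are reported, all three fall away.

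**What remains.** Exact (Clopper-Pearson) 95% limits for *x* of 10 are the 0.025 quantile of Beta(*x*, 11 − *x*) and the 0.975 quantile of Beta(*x* + 1, 10 − *x*). For 10 of 10 the lower limit is 0.025^(1/10) and the upper limit is 1.

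| Assumed count | Lower | Upper |
|---|---|---|
| 8/10 | 0.444 | 0.975 |
| 9/10 | 0.555 | 0.997 |
| 10/10 | 0.692 | 1 |

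These widths come from the sample size. They are the same whether or not the measure was named in advance.

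**The case for a change.** The strongest case for a change is that a stated objective, listed ahead of the comparison, has no defined analysis. One paragraph and one table would supply it at almost no cost, and no threshold need be imposed: the plan could simply say that estimates will be reported. The general rule is no full answer, because it fixes format and not content. Nothing at this point in the text is marked as removed.

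The factual part stands. No measure or denominator is named, and acceptability is the weaker half, since the survey content is not listed and no item can be tied to it.

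Three things limit what follows:

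- The document is brief throughout. It does not list the secondary outcomes either, so silence about (a) is not a sign of selective planning.
- It describes analyses already done. Whether any criterion was chosen after results were known cannot be told from it, and new wording now could disclose choices but not restore prespecification.
- The easiest measure to add, the share of the 10 with post-treatment fatigue scores, is retention for assessment. Someone can stop exercising and still attend testing, or take every call and miss it. Writing that measure into the plan would not settle whether telephone delivery is feasible or acceptable.

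Possible loss between consent and randomisation a week later is a fair point about denominators, but the documents report no such loss and the usual participant flow counts would show it.

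**Conclusion.** This is missing detail that analysts fill sensibly, not an error. No stated rule or number gives a wrong result, and every output for objective (b) is the same with or without named feasibility measures. Flow counts and retention fit the descriptive rule already in the SAP. Adherence and acceptability can be reported where records exist, and left as unanswered where they do not.

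The supportable size is the imprecision at 10 in the telephone arm: 44% to 97%, 55% to 100% and 69% to 100% for assumed counts of 8, 9 and 10. A change to the plan would not improve it. The larger figures, such as a pass probability ranging from 38% to 88% at 80% true retention, rest on a pass/fail decision that is not in the plan.

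The conclusion assumes that feasibility is reported as estimates. If a report did call the programme feasible against a cut, readers should treat that cut as post hoc, because these documents set none.

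### Does simple randomisation of only 20 participants put the 10:10 comparison at risk?

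*Combined protocol and SAP*

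**What the plan says.** Under Randomization and Allocation Concealment, the protocol states that "Simple randomization (i.e., single random number sequence) using SPSS was performed by the UM study team". It reports that participants were "randomly assigned into the telephone-delivered exercise group (telephone; n=10) or the in-person-delivered exercise group (in-person; n=10"). On concealment, "sealed envelopes with group assignment were given to the study team at WSU and pulled sequentially at the time of randomization"; the team that made the list took no part in testing or training.

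Testing Sessions gives the timing. "At baseline visit 1, participants completed informed consent procedures and surveys using Qualtrics", and one week later they "returned their accelerometer, and were randomized into either telephone or in-person group".

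The Statistical Analysis Plan has two uses for the arm sizes. By arm, "Mean change scores (SD) (pre-post intervention) were calculated for each variable by intervention group", with effect sizes that are then used to size a further study. Between arms, "Between-group differences were analyzed using a two-sample t test to generate mean differences and 95% confidence intervals".

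No block, stratification, fixed total or arm-closing rule is described, and no power, margin or effect size is given as the basis for 20 participants.

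**The concern.** Simple randomisation in its usual sense treats each assignment as a separate coin toss, so arm sizes are left to chance. In a large trial this hardly matters. With 20 people the arms can easily end at 7:13 or 6:14. With a common SD, the two-sample t test is most precise at equal arms, and a small arm also makes its own mean change and effect size less precise. Those effect sizes feed the sample size of the next study. A random permutation of ten telephone and ten in-person assignments would remove this risk for the price of a different list. On first reading, the plan seems to name a method that does not secure the arm sizes it quotes.

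**Working it through.** **Inputs.** N = 20, ten per arm (Randomization and Allocation Concealment); a two-sample t test with 95% CI (Statistical Analysis Plan). Assumptions: independent assignments with probability 0.5, and a common SD of change in both arms. The plan states no figure for N=20 that could be reproduced, only the 10/10 split.

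**1. How likely is each split?** P(10:10) = C(20,10)/2^20 = 184,756/1,048,576 = 17.6%. The SE of the group difference is SD × √(1/n1 + 1/n2), which at 10:10 is 0.447 SD.

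| Split | Probability | SE relative to 10:10 |
|---|---|---|
| 10:10 | 17.6% | 1.000 |
| 9:11 | 32.0% | 1.005 |
| 8:12 | 24.0% | 1.021 |
| 7:13 | 14.8% | 1.048 |
| 6:14 | 7.4% | 1.091 |
| 5:15 | 3.0% | 1.155 |

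The split is 8:12 or closer in 73.7% of cases, where the SE penalty is at most 2.1%. It is 7:13 or worse in 26.3%, and 6:14 or worse in 11.5%.

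**2. What is the average cost before randomisation?** Weighting by these probabilities:
- The mean SE ratio is 1.028 and the mean variance ratio 1.060. The latter is worth 20 × 0.06 = 1.2 participants.
- The between-group 95% half-width is t(0.975, 18) × √(1/n1 + 1/n2): 0.940 SD at 10:10 and 0.966 SD on average. Both intervals are very wide.
- The single-arm 95% half-width, t(0.975, n−1)/√n, is 0.715 SD at n=10 and 0.748 SD on average (+4.6%).
- Power at assumed true differences of 0.5, 0.8 and 1.0 SD is 18.5%, 39.5% and 56.2% at 10:10, against 17.8%, 37.9% and 54.0% on average under simple randomisation. The gap is 0.7 to 2.2 percentage points.
- The chance of a baseline fatigue gap of at least 0.5 SD (normal, known SD) is 26.4% at 10:10 and 27.7% under simple randomisation. Fixing arm sizes hardly touches covariate balance.

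**3. What was the cost in this trial?** The protocol reports ten and ten. At 10:10 the SE ratio is 1.000, so the loss is zero, however the list was made.

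**4. Was it coin-tossing at all?** The description of a single sequence also fits 20 random numbers sorted and cut in half. Take the two arms of ten as realised, and give coin-tossing and a fixed list equal prior weight. The chance of a fixed list is then 1/(1 + 0.176) = 85%. With a prior of only 20% it is 0.2/(0.2 + 0.8 × 0.176) = 59%. These priors are illustrative, but the shuffled list may well be what was used.

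**5. What would the alternative cost?** With one 10/10 list, someone who always guesses the arm that is behind is right on average 10 + (4^10/C(20,10) − 1)/2 = 12.3 times in 20, against 10.0 under simple randomisation. If the totals are known, the last 20/11 = 1.8 assignments on average are certain.

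**The case for a change.** The best case for raising the point is that the average understates it. What a fixed list removes is the tail: an 11.5% chance of 6:14 or worse, and a single-arm half-width 29% wider when an arm has seven people (0.925 against 0.715 SD). Since the analysis plan carries by-arm effect sizes forward into a sample size calculation, a thin arm could mislead the next study. The predictability cost is also contained: another site makes the list, envelopes are sealed, and each person's eligibility, consent, surveys and gait speed are settled at or before the first visit, a week before allocation. And a reader cannot tell from the text which kind of list was used.

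The arithmetic stands, and as advice for a future small trial the permuted list is sound. But the tail did not occur at ten per arm. The week's gap protects the participant already enrolled; it does not stop someone who has counted earlier assignments from being influenced when the next person is screened. Telephone and in-person delivery are plainly distinguishable, and the investigators themselves decide eligibility. A team that values unpredictability above roughly 3% in standard error can defend simple randomisation. The ambiguity of the label is real, but it is a matter of description.

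**Conclusion.** The concern does not hold. Simple randomisation is valid and unbiased, and the reported 10:10 split is the one the alternative would have guaranteed, so the loss of precision in this trial is nil on either reading the text supports: an achieved split or a list with fixed totals. Only if ten per arm had been a target that was missed would there be a loss. The documents give no sign of that; on the assumptions above, the average SE penalty would then be 3.5% (mean ratio 1.035 over unequal splits), and the t test would still be valid. Considered before randomisation, the choice is between about 2.8% in average SE and about 2.3 extra correct guesses in 20, with no stated power target or margin at stake and objectives of feasibility and a descriptive comparison. That is a trade-off within the designers' discretion. What is left is whether the word simple accurately labels the list, which affects how the method is described and nothing the trial does or concludes. The figures assume independent 50:50 assignments and equal SDs; the conclusion for this trial rests on taking the past-tense report of ten per arm at face value.

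### The arms are compared by an unadjusted t test, apparently on pre-post change; adjusting for the baseline already collected would usually narrow the interval and deal with chance imbalance at 10 per arm

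*Combined protocol and SAP*

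**What the plan says.** Objective (b) compares telephone with in-person delivery "in pre- to post-treatment changes in fatigue and secondary outcomes". In the Statistical Analysis Plan, "Mean change scores (SD) (pre-post intervention) were calculated for each variable by intervention group"; the arms are then compared as follows: "Between-group differences were analyzed using a two-sample t test to generate mean differences and 95% confidence intervals". That sentence does not say whether the test is run on change scores or on post-treatment scores. Read with the change-score sentence and the objective, change is the natural reading. No covariate, ANCOVA or other regression appears anywhere.

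The baseline values exist. Under Testing Sessions, "At baseline visit 1, participants completed informed consent procedures and surveys using Qualtrics"; gait speed is also measured at that visit, and an accelerometer is worn for the week before randomisation at baseline visit 2. After eight weeks, "participants completed a post-treatment testing session, which included Qualtrics surveys, gait speed assessment, and donning of a PRO-Diary". Under Randomization and Allocation Concealment, 10 people are given for each arm, and "Simple randomization (i.e., single random number sequence) using SPSS was performed by the UM study team". No stratification is described.

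**The concern.** A change score does correct for baseline, but with the slope of post on pre fixed at 1. If the true slope is below 1, subtracting the whole baseline over-corrects. Part of any chance baseline difference between the arms is then carried, with opposite sign, into the estimated treatment difference. Over all randomisations this averages to zero. In the one trial that is run it does not, and its direction can be read from the observed baseline means. With 20 people allocated by simple randomisation, that baseline difference can be sizeable.

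The mean difference and its 95% interval are the trial's answer to objective (b). At stake are the width of that interval and whether it can be taken at face value when the arms start apart. Feasibility and acceptability, objective (a), have no baseline value and are not touched by this point.

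**Working it through.** The documents give no power calculation, expected interval width or pre/post correlation, so there is no figure of theirs to reproduce.

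**Inputs from the documents.** n = 10 per arm, N = 20, simple randomisation, one baseline and one post-treatment measurement, 95% intervals.

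**Assumptions.** Normal data, equal pre and post SD (set to 1), a common linear slope equal to rho, no dropout. Rho is not given, so a range is shown.

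**1. Expected width.** The square root of the expected squared half-width is:

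- Change-score t test (18 df): t18 × √(2(1 − rho)) × √(2/10), with t18 = 2.101.
- ANCOVA (17 df): t17 × √(1 − rho²) × √((2/10) × 17/16), with t17 = 2.110. The factor 17/16 = (N − 3)/(N − 4) is the cost of estimating the slope.

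At rho = 0.5, change gives 2.101 × 1 × 0.447 = 0.940. ANCOVA gives 2.110 × 0.866 × 0.461 = 0.842. The ratio is 0.896.

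The two are equal when (t17/t18)² × (1 + rho)/2 × 17/16 = 1, that is, at rho = 0.867.

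Simulation (200,000 trials per setting, 10 per arm, no arm effect) gives the mean half-widths directly. They are slightly smaller than the formula values because a mean SD lies below the root of the mean variance.

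| rho | Half-width, change (SD) | Half-width, ANCOVA (SD) | ANCOVA interval on average | Single trials in which ANCOVA's interval is wider |
|---|---|---|---|---|
| 0.3 | 1.10 | 0.91 | 17% narrower | 10% |
| 0.5 | 0.93 | 0.83 | 10% narrower | 20% |
| 0.7 | 0.72 | 0.68 | 5% narrower | 38% |
| 0.8 | 0.59 | 0.57 | 2% narrower | about 49% |
| 0.9 | 0.41 | 0.42 | 0.7% wider | about 64% |

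**2. How often the arms start apart.** The SD of the baseline mean difference D is √(2/10) = 0.447. So P(|D| > 0.5) = 2 × (1 − Φ(0.5/0.447)) = 0.264.

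**3. What a baseline difference does to the change-score estimate.** Given D, the estimate is shifted by −(1 − rho) × D. For D = 0.5:

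| rho | Size of shift (SD) | Share of change-score half-width |
|---|---|---|
| 0.3 | 0.7 × 0.5 = 0.35 | 0.35/1.10 = 32% |
| 0.5 | 0.5 × 0.5 = 0.25 | 0.25/0.93 = 27% |
| 0.7 | 0.3 × 0.5 = 0.15 | 0.15/0.72 = 21% |
| 0.8 | 0.2 × 0.5 = 0.10 | 0.10/0.59 = 17% |

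**4. Coverage of the 95% interval, simulated.**

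| rho | Change, all trials | Change, abs(D) > 0.5 SD | Change, other trials | ANCOVA, either group | ANCOVA width against change when abs(D) > 0.5 SD |
|---|---|---|---|---|---|
| 0.3 | 95% | 89% | 97% | 95% | 12% narrower |
| 0.5 | 95% | 90% | 97% | 95% | 6% narrower |
| 0.7 | 95% | 92% | 96% | 95% | equal |
| 0.8 | 95% | 93% | 96% | 95% | 3% wider |

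The groups reconcile. At rho 0.3, non-coverage is 0.264 × 0.113 + 0.736 × 0.028 = 0.050.

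**5. Sensitivity for fatigue.** Entry requires that participants "had significant fatigue as indicated by a score of ≥ 36", which could restrict baseline spread. If baseline variance were halved with slope and residual variance unchanged (an assumption), ANCOVA's mean interval is 8%, 4% and 1% narrower at slopes 0.3, 0.5 and 0.7, and 0.6% wider at 0.8.

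**The case against.** The strongest reply is that nothing here is wrong. A t test on change answers objective (b) directly, keeps 95% coverage over randomisations, and belongs to a 20-person study whose first aim is feasibility. That stands, and it limits the point to a suggested improvement.

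The gain also rests on a correlation that the documents do not report. At rho 0.8 it is a coin toss which interval is narrower in a given trial. That stands too: at high rho the benefit is in conditional bias, not in width.

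Nor does ANCOVA clear away imbalance exactly in each trial. It replaces a fixed slope error of 1 − rho (0.50, 0.30 and 0.20 at rho 0.5, 0.7 and 0.8) with an estimation error of SE about √((1 − rho²)/16), that is 0.22, 0.18 and 0.15. The error is zero on average and smaller than the fixed one at these values, and the ANCOVA interval allows for it. Only the adjusted variable is covered, and a common slope is hard to check at 10 per arm.

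The FSS sensitivity is tentative. FSS is described only as an entry criterion, and the fatigue scores named for plotting are intensity and interference. Restriction might instead lower rho, which would favour ANCOVA.

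Finally, the plan is written in the past tense. If results had been seen, changing the main analysis would be post hoc and should be declared as such. Keeping the t test alongside lets a reader see both. The planned individual fatigue plots would show an imbalance, but would not correct the estimate for it.

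**Conclusion.** The point holds, as an improvement to consider. The planned comparison, read as a t test on change, is valid overall. Adjusting for the baseline already measured would be better on two counts:

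- **Precision.** A gain in average interval width for any rho below about 0.87, worth having at 0.3 to 0.5, small at 0.7 and near nil at 0.8.
- **Conditional validity.** Coverage restored to 95% in the roughly one trial in four that starts more than 0.5 SD apart.

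The algebra and simulation are firm under normality, equal variances and a common linear slope. The size of the benefit in this trial is not known, because rho is not known and may differ between outcomes. The choice of change scores is itself inferred. If the t test is on post-treatment scores, the case for adjustment remains, with a large-sample variance ratio of 1 − rho² in ANCOVA's favour.

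**What to change.** For each outcome measured before and after treatment, regress the post-treatment value on arm and that variable's own baseline, and report the adjusted mean difference with its 95% interval as the main between-group result. The arm contrast is the same whether post score or change is the dependent variable, so the question in objective (b) is unchanged. State in the SAP that the t test is on change scores, and keep it as a sensitivity analysis. If any between-group results were seen before the change, say so.

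The cost is a sentence of SAP text and one regression command per outcome, with no new data. One degree of freedom is lost, which widens the interval on average only above rho of about 0.87, or from a slope of about 0.8 if baseline variance is halved.
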